5.5.1.5. Baseline and Postbaseline Definition

Table CGAI.5.4 describes the rules for determining the patient population and baseline and postbaseline observations for each study phase and type of analysis. When "last of Visit x-x" is used in the table, the last nonmissing observation obtained in the visit interval will be used.

Table CGAI.5.4. Patient Population with Baseline and Postbaseline Definitions by Study Period and Type of Analysis

Study Period / Analysis	Patient Population	Baseline Observation	Postbaseline Observation(s)
Study Period III			
Efficacy analyses (Repeated Measures) or average of observed monthly values	ITT Population with a baseline and at least 1 postbaseline observation	Visit 3	All scheduled visits 3 < Visits ≤7
Efficacy analyses at LOCF endpoint		Visit 3	Last of Visit 3.01-7
Quality of Life analyses (Repeated Measures)		Visit 3	All scheduled visits 3 < Visits ≤7
Quality of Life analyses at LOCF endpoint or for average of observed monthly values		Visit 3	Last of Visit 3.01-7
TEAEs	Safety Population	All Visits 1–3	All Visits 3.01–7
Serious Adverse Events, Discontinuations due to Adverse Events	Safety Population	NA	All Visits 3.01–7
C-SSRS categorical analyses	Patients with a baseline and at least 1 postbaseline C-SSRS assessment	Recent History: Visits 1–3 excluding lifetime ^a All Prior History: Visits 1–3 including lifetime ^a	All Visits 3.01–7
Treatment-emergent abnormal laboratory values	Safety Population with normal laboratory values at all nonmissing baseline visits (with respect to direction being analyzed) and who have at least 1 postbaseline observation	Low: Minimum from Visits 1–3 High: Maximum from Visits 1–3 Abnormal: All Visits 1–3	Low: Minimum from Visits 3.01–7 High: Maximum from Visits 3.01–7 Abnormal: All Visits 1–3
Treatment-emergent immunogenicity	Safety Population	Visit 3	All Visits 3.01–7
Treatment-emergent changes in temperature and weight	Safety Population with a baseline and at least 1 postbaseline observation	Low: Minimum from Visits 1–3 High: Maximum from Visits 1–3	Low: Minimum from Visits 3.01–7 High: Maximum from Visits 3.01–7
Treatment-emergent changes in blood pressures, pulse, and ECGs	Safety Population with a baseline and at least 1 postbaseline observation	Low: Last non-missing from Visits 1–3 High: Last non-missing from Visits 1–3	Low: Minimum from Visits 3.01–7 High: Maximum from Visits 3.01–7

Patient Population with Baseline and Postbaseline Definitions by Study Period and Type of Analysis

Study Period / Analysis	Patient Population	Baseline Observation	Postbaseline Observation(s)
Study Period III	•	.	
Continuous safety analyses (Repeated Measures)	Safety Population with a baseline and at least 1 postbaseline observation	Last of Visits 1–3	All scheduled visits 3 < Visits ≤7
Continuous safety analyses – change from baseline to LOCF endpoint (ANCOVA)	Safety Population with a baseline and at least 1 postbaseline observation	Last of Visits 1–3	Last of Visits 3.01–7
Study Period IV			
TEAEs	Open Label treatment Population	All Visits 1-7	All Visits 7.01–16
Serious Adverse Events, Discontinuations due to Adverse Events	Open Label treatment Population	NA	All Visits 7.01–16
Treatment-emergent abnormal laboratory values	Open Label treatment Population and Patients with normal laboratory values at all nonmissing baseline visits (with respect to direction being analyzed) and who have at least 1 postbaseline observation	Low: Minimum from Visits 1–7 High: Maximum from Visits 1–7 Abnormal: All Visits 1–7	Low: Minimum from Visits 7.01-16 High: Maximum from Visits 7.01-16 Abnormal: All Visits 7.01-16
C-SSRS categorical analyses	Open Label treatment Population and Patients with a baseline and at least 1 postbaseline C-SSRS assessment	Recent History: All Visits 1–7 excluding lifetime ^a All Prior History: Visits 1 – 7 including lifetime ^a	All Visits 7.01–16
Treatment-emergent immunogenicity	Open Label treatment Population	Visit 3	All Visits 7.01–16
Treatment-emergent changes in temperature and weight	Open Label treatment Population and Patients with a baseline and at least 1 postbaseline observation	Low: Minimum from Visits 1–7 High: Maximum from Visits 1–7	Low: Minimum from Visits 7.01–16 High: Maximum from Visits 7.01–16
Treatment-emergent changes in blood pressures, pulse, and ECGs	Open Label treatment Population and Patients with a baseline and at least 1 postbaseline observation	Low: last non-missing from Visits 1–7 High: last non-missing value from Visits 1–7	Low: Minimum from Visits 7.01–16 High: Maximum from Visits 7.01–16

Patient Population with Baseline and Post-baseline Definitions by Study Period and Type of Analysis

			Postbaseline
Study Period / Analysis	Patient Population	Baseline Observation	Observation(s)
Study Period V			
TEAEs	Post-treatment Population	All Visits 1- 16	All Visits 16.01–18
Serious Adverse Events, Discontinuations due to Adverse Events	Post-treatment Population	NA	All Visits 16.01–18
Post-treatment-emergent abnormal laboratory values	Post-treatment Population and Patients with normal laboratory values at all nonmissing baseline visits (with respect to direction being analyzed) and who have at least 1 postbaseline observation	All Visits 1- 16	All Visits 16.01–18
C-SSRS categorical analyses	Post-treatment Population and Patients with a baseline and at least 1 postbaseline C-SSRS assessment	Recent History: All Visits 1–16 excluding lifetime ^a All Prior History: Visits 1 – 16 including lifetime ^a	All Visits 16.01–18
Treatment-emergent immunogenicity	Post-treatment Population	Visit 3	All Visits 16.01–18
Post-treatment-emergent changes in temperature and weight	Post-treatment Population and Patients with a baseline and at least 1 postbaseline observation	Low: Minimum from Visits 1–16 High: Maximum from Visits 1–16	Low: minimum from Visits 16.01–18 High: maximum from Visits 16.01–18
Post-treatment-emergent changes in blood pressures, pulse, and ECGs	Post-treatment Population and Patients with a baseline and at least 1 postbaseline observation	Low: last non-missing from Visits 1–16 High: last non-missing from Visits 1–16	Low: minimum from Visits 16.01–18 High: maximum from Visits 16.01–18

Patient Population with Baseline and Post-baseline Definitions by Study Period and Type of Analysis

Study Periods III / IV Combined		-	
Efficacy analyses	ITT Population with a baseline and at least 1 postbaseline observation	Visit 3	All scheduled visits 3 < Visits ≤16
Quality of Life analyses	ITT Population with a baseline and at least 1 postbaseline observation	Visit 3	All scheduled visits 3 < Visits ≤16
Treatment-emergent immunogenicity	Safety Population	Visit 3	All Visits 3.01–16
Continuous safety analyses (Repeated Measures) Study Periods III/ IV/V Combined	Safety Population with a baseline and at least 1 postbaseline observation	Visit 3	All scheduled visits 3 < Visits ≤16
Efficacy analyses	ITT Population with a baseline and at least 1 postbaseline observation	Visit 3	All scheduled visits 3 < Visits ≤18
Quality of Life analyses	ITT Population with a baseline and at least 1 postbaseline observation	Visit 3	All scheduled visits 3 < Visits ≤18
Continuous safety analyses (Repeated Measures)	Safety Population with a baseline and at least 1 postbaseline observation	Visit 3	All scheduled visits 3 < Visits ≤18
Treatment-emergent immunogenicity	Safety Population	Visit 3	All Visits 3.01–18

Abbreviations: ANCOVA = analysis of covariance; C-SSRS = Columbia Suicide Severity Rating Scale; ECG = electrocardiogram; eCRF = electronic case report form; ITT = intent-to-treat; LOCF = last observation carried forward; TEAE = treatment-emergent adverse event.

Note: Visit 3.01 indicates the first unscheduled visit occurring after Visit 3 and prior to Visit 4. Visit 7.01 indicates the first unscheduled visit occurring after Visit 7 and prior to Visit 8. Visit 16.01 indicates the first unscheduled visit occurring after Visit 16 and prior to Visit 17.

^a Lifetime is captured in the C-SSRS Visit 1 eCRF.

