Study Period IV: Patients who complete the double-blind treatment phase (Study Period III) can opt to enter an open-label treatment period (Study Period IV) for up to 9 months of treatment with LY2951742. Sites and patients will remain blinded to patients' previous treatment assignments. All patients entering the open-label period will receive an initial dose of 240 mg of LY2951742 at Visit 7 and will remain at the office for a 30-minute post-injection observation at this visit. Injections after Visit 7 will not require an observation period. At Visit 8, all patients will receive a 120 mg dose of LY2951742; dosing at subsequent visits (beginning at Visit 9) will be flexible (either 120 mg or 240 mg/month) at the discretion of the investigator. Dosing and dose changes can only occur at regular visits (once monthly). Patients will continue to have efficacy and safety assessed, including daily completion of the ePRO diary (see Appendix 2,

Schedule of Activities). Patients may continue to take their allowed acute migraine headache medication as in Study Period III.

Study Period V: Patients who discontinue from Study Period III or IV must enter directly into Study Period V for assessment during washout of investigational study drug. During this 4-month phase, sites and patients will continue to remain blinded to patients' original doubleblind treatment assignments. Patients will follow all study procedures during Study Period V but will not receive investigational product. One month after Visit 16, if clinically warranted due to a worsening of symptoms, patients may start migraine prevention medication(s) at the discretion of the investigator (Section 6.6.1). The list of allowed preventive medications is provided in Section 6.8. At Visit 18 (Month 16), patients will return to the site for their last study visit and discharge from the study.

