4.3. Scientific Rationale for Study Design

The length of the randomized, double-blind treatment phase (3 months) is considered a sufficient duration to assess the safety and efficacy of a migraine prevention medication given the mechanism and observed onset of action for CGRP antibodies (Dodick et al. 2014a, 2014b). Furthermore, a placebo-controlled study with a duration longer than 3 months may not be tolerated by patients suffering from chronic migraine. A 4-month post-treatment follow-up phase is included to evaluate patient safety during wash-out of LY2951742. This allows for a total of 5 months of observation from the time of last injection of LY2951742. A 5 -month post-treatment observation period allows for a wash-out of approximately 5 elimination half-lives of LY2951742 and should decrease LY2951742 serum concentrations by approximately 97% during this time.

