6.9.2. Continued Access

Investigational product will not be made available to patients after conclusion of this study.

7. Discontinuation Criteria

Patients who discontinue the study or investigational product during the double-blind treatment phase (Study Period III) or open-label treatment (Study Period IV) will proceed immediately to Study Period V.

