5.5.5. Exposure to Investigational Medicinal Product

Patients will receive the investigational medicinal product (IMP) at the following planned time points:

- Beginning of Month 1 (Visit 3)
- Beginning of each month from Month 2 to Month 11 (Visit 5 to Visit 15)

The following information will be recorded on the eCRF for each dose:

• Confirmation that the patient received the IMP (including reason if the IMP was not given)

• Date and time of administration

The following will be derived from the information recorded on the eCRF:

- For double-blind treatment phase (SP III), duration of exposure in days is calculated as treatment phase disposition date – first date IMP administered +1
- For open label phase (SP IV), duration of exposure in days is calculated as open label disposition date first date IMP administered during SP IV +1.
- For double-blind treatment phase (SP III), number and percentage of patients with 1 dose, 2 doses, and 3 doses injected.
- For open label phase (SP IV), number and percentage of patients with 1 dose, 2 doses, 3 doses,, 8 doses, and 9 doses injected.

Comparisons between treatments for duration of IMP exposure will be performed using an ANOVA with treatment, baseline medication overuse (yes versus no) and concurrent prophylaxis (yes versus no) in the model. The number of patients with 1 dose, 2 doses, 3 doses, 4 doses, 5 doses, 6 doses, 7 doses, 8 doses, ..., 12 doses injected will be summarized. The number of patients with 1 dose, 2 doses, and 3 doses will be compared between treatment groups with CMH test. In addition, injections not administered with the corresponding reasons will be listed.

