5.5.12.1. Categorical Safety Variables

Unless specified otherwise, the categorical safety analyses will include both scheduled and unscheduled visits. Categorical safety analyses will only be conducted for SP III, SP IV, SP V, and SP III/IV separately.

Comparisons between treatment groups for all categorical safety measures will be made using CMH test for SP III, and SP III/IV with the ITT population.

Descriptive statistics only will be presented for the treatment groups in SP IV and SP V.

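### The double-blind adverse event window has no post-dose tail, so patients who stop mid-interval are followed for less time after their last dose than completers

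*SAP*

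**What the plan says.** **The double-blind window.** SAP Section 5.5.1.5, Table CGAI.5.4, takes SP III TEAEs, SAEs and discontinuations due to adverse events from "All Visits 3.01–7". No days are added after the last dose. SP III exposure also ends at disposition: it is the "treatment phase disposition date – first date IMP administered +1" (SAP Section 5.5.5).

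**Where a stopper goes.** Protocol Section 4.1: "Patients who discontinue from Study Period III or IV must enter directly into Study Period V". Protocol Section 7 repeats that patients who stop in SP III or IV "will proceed immediately to Study Period V". Early-termination procedures come first (protocol Section 7.1.1).

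**What happens to later events.** In Table CGAI.5.4 the SP V adverse event window is "All Visits 16.01–18", and an event is treatment-emergent there only if new or worse than a baseline of "All Visits 1- 16". SAP Section 5.5.12.1 tests categorical safety between arms for SP III and SP III/IV, then adds: "Descriptive statistics only will be presented for the treatment groups in SP IV and SP V". SAP Section 5.5.12 limits the combined SP III/IV/V period to MMRM change and time-to-event analyses, and no time-to-event analysis of adverse events is specified. SAP Section 5.8.1.2 lists TEAE reports at interim analysis #2 for SP III and SP IV. It treats the double-blind results at that point as final. Only anti-drug antibody analyses reach into SP V there.

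**Persistence of the drug.** Protocol Section 4.3 says that five months of observation after the last injection "allows for a wash-out of approximately 5 elimination half-lives of LY2951742", with serum concentrations down by about 97%.

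**The concern.** SP III is the only placebo-controlled period, so its adverse event tables carry the randomized safety comparison. Within it, follow-up after the last dose depends on whether the patient stayed. A completer is followed from Visit 6 to Visit 7, about 30 days. A patient who terminates early 3 or 14 days after an injection is followed for about that long, with most of the dose still present.

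A new event in the remainder of that interval enters no between-arm comparison. SP V cannot stand in for one, because patients who went through open label, including former placebo patients, have by then received LY2951742.

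Stopping can also be informative. Protocol Section 7.1.1 requires it for certain possibly related serious events and liver abnormalities.

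The gap matters most for late-onset events. SAP Section 5.5.12.1.1 classifies hypersensitivity and injection-site events by timing, with categories through 14 days and beyond 14 days after dosing. Someone who leaves a few days after an injection cannot contribute to the later categories in SP III.

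**Working it through.** **Inputs.** About 5 half-lives in 5 months and a 97% fall (protocol 4.3). Double-blind injections at Visits 3, 5 and 6, about 30 days apart, with Visit 7 30 ± 2 days after Visit 6 (protocol Appendix 2). Deviation limits of 21 to 37 days between doses (SAP Section 7). N = 1140 as 570/285/285, with 15% discontinuation (SAP 5.2).

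**1. Half-life.** 5 months / 5 = about 30 days. Check against the protocol's own figure: 1 − 0.5^5 = 96.9%, which reproduces the stated 97%.

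**2. Share of the last dose remaining, 0.5^(t/30).**

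| Days since last dose | Remaining |
|---|---|
| 3 | 93% |
| 7 | 85% |
| 14 | 72% |
| 30 | 50% |
| 32 | 48% |
| 37 | 42% |

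With an assumed half-life of 25 to 33 days, the 30-day figure runs from 44% to 53% and the 14-day figure from 68% to 75%. This is first-order elimination of the last dose alone. It ignores absorption, and carry-over from earlier doses would raise the total.

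**3. Patients affected at 15%.** 0.15 × 1140 = 171: about 86 on placebo (0.15 × 570) and about 43 per dose arm (0.15 × 285).

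**4. Person-time removed relative to a completer's 30-day tail.** Only the unobserved rest of the last dosing interval counts.
- All stops at dosing visits: each stopper has already had the full interval, so 0 days are lost (0%).
- Stops spread evenly over 90 days: each loses 15 of 30 days on average, so 0.15 × 15/90 = 2.5% of planned SP III person-time. Per dose arm this is 43 × 15 = 645 patient-days out of 285 × 90 = 25,650.
- The same even spread at an assumed 5% or 10% discontinuation gives 0.05 × 15/90 = 0.8% or 0.10 × 15/90 = 1.7%.

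These are two timing scenarios. The arithmetic ceiling, with every stop straight after an injection, would be 0.15 × 30/90 = 5%, but nothing in the documents points to that pattern.

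**The case against.** Attribution by study period is prespecified and coherent, and the events are not lost to the study. Adverse events are collected at Visits 17, 18 and early termination and are summarised for SP V. Events that cause stopping begin before it, so they are counted in SP III, which also has its own row for discontinuations due to adverse events. The planned analysis is the percentage of patients with an event, so lost person-time does not translate directly into lost incidence. All of this stands, and it limits the point to new or worsened events between early termination and the end of the last dosing interval.

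A reader might infer more, in four ways that the documents do not support.
- **That 7.5% of person-time is lost** (0.15 × 45/90). This counts all time from stopping to day 90, including months in which no dose was given. Measured against a completer's post-dose follow-up, the even-spread figure is 2.5%.
- **That at least half of the dose always remains when the window closes.** This holds up to about 30 days. At 32 to 37 days the share is 48% to 42%, and a completer at Visit 7 also has about 50%.
- **That the window shuts on the day of stopping.** The SAP sets windows by visit number and gives no cut-off date. The early-termination visit is the practical boundary.
- **That event rates on LY2951742 are understated.** This needs more stopping on drug than on placebo, and no document says so. Stopping for lack of effect could be commoner on placebo.

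What the objection does not answer is the unequal follow-up after the last dose, or the absence of any table that would show whether it matters.

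**Conclusion.** The point holds as an asymmetry in follow-up of modest size. At 15% discontinuation, 0% to about 2.5% of planned SP III person-time within one dosing interval of the last injection falls outside the randomized comparison, depending on whether stops cluster at dosing visits. The even-spread case is about 645 patient-days per dose arm. The direction of any bias is unknown.

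This rests on a half-life of about 30 days derived from approximate protocol figures, on 15% as a planning assumption (the documents give no actual counts or timing of stops), and on the early-termination visit as the end of SP III. Primary efficacy is unaffected. The size does not justify replacing the main window or extending it to the planned Visit 7 date, which would add time without treatment and possibly time on another preventive. A supportive analysis is justified: it is cheap, and the gap falls in the only placebo-controlled safety comparison.

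**What to change.** Add to SAP Section 5.5.12.1.1, and to the interim analysis #2 reports in Section 5.8.1.2, a by-arm SP III comparison of TEAEs, SAEs and special-topic events (hypersensitivity, injection site). It should:
- count events by onset date, up to 30 days after the last double-blind injection and before any open-label dose, whatever visit label they carry;
- judge treatment emergence against the Visits 1–3 baseline;
- stand beside the current Visits 3.01–7 tables.

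The cost is SAP wording and programming. Injection dates are on the eCRF (SAP Section 5.5.5) and adverse events are collected in SP V. Onset dates are assumed to be available, as the planned hypersensitivity listing by time since the latest dose already requires. There is a precedent: the immunogenicity window in Table CGAI.5.4 runs across periods, from Visit 3.01 to Visit 18.

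There are two downsides. Some events after stopping are included. Ascertainment in SP V is also sparser, with visits 60 days apart, and depends on patients entering that period. Protocol Section 4.1 makes entry mandatory while Sections 7.1.1 and 7.1.4 only request it, so those passages should be reconciled. The table should report how many stoppers in each arm contributed SP V data. No change to treatment or clinical management is implied.

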^a The eligibility period of the prospective baseline assessment will last from 30 to 40 days. Investigators and patients may have up to an additional 5 days to schedule their Visit 3 appointment (beyond the 40 days); however, eligibility will be based on the 30- to 40-day period.

^b Visit is to include a review of any spontaneously reported adverse events and collection of blood samples for immunogenicity, PK, and CGRP plasma.

^c A neurological exam will be conducted at screening, Month 3 (final visit of double-blind treatment), Months 6, 9, and 12 (open-label treatment), and Month 16/early termination in order to assess for any signs of pre-existing or treatment-emergent neurological abnormalities such as stroke or other cerebrovascular events.

^d Electrocardiograms (ECGs) will be performed at Visit 1, Visit 3, Visit 7, Visit 10, Visit 16, and Visit 18 or early termination. Note: The Visit 3 ECG should be collected prior to blood draws and dosing. Patients must be supine for approximately 5 to 10 minutes before ECG collection and remain supine but awake during ECG collection.

^e Vital signs taken at every office visit will include body temperature, blood pressure and pulse. Blood pressure and pulse will be measured in triplicate in the sitting position and should be measured prior to blood draws. Blood pressure will be assessed by utilizing a calibrated machine.

^f Chemistry labs collected at Visit 3, Visit 7, Visit 10, Visit 13, Visit 16, and Visit 18 or early termination must be fasting. Fasting is defined as no food or drink, except water, for at least 8 hours prior to testing.

g In the event of a positive urine leukocyte esterase result, a repeat urine sample will be collected and shipped to the central laboratory.

^h A positive urine test must be followed by a serum pregnancy test for confirmation.

Immunogenicity and storage sample, and PK blood sampling to be performed at the indicated visits and prior to dose administration if the visit is a dosing visit. Samples will be taken in the event of early termination. Immunogenicity samples also may be collected in the event of a systemic allergic/hypersensitivity reaction (see Section 8.4.3). The exact date and time of the samples should be recorded.

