5.3. Randomization and Treatment Assignment

Patients will be randomized in a 2:1:1 ratio to placebo, LY2951742 120 mg/month, or 240 mg/month. Randomization will be stratified within country and by acute headache medication overuse (yes versus no), and use of concurrent migraine prophylactic medication (yes versus no).

^a Patients randomized to the 120 mg dose will receive a loading dose of 240 mg at the first injection only (Visit 3).

^b At Visit 7, all patients who enter the open-label extension will receive LY2951742 at a dose of 240 mg.

^c At Visit 8, all patients will receive LY2951742 at a dose of 120 mg.

d Starting at Visit 9, patients will have the option to receive either LY2951742 dose of 120 mg or 240 mg (flexible dosing).

The acute headache medication overuse will be based on the frequency of acute headache medication intake during the 30-day baseline, and will be adapted from Section 8.2 of the ICHD-3 beta guidelines (ICHD-3 2013).

To ensure an appropriate balance of patients with concurrent prophylaxis use, the sponsor will stop enrollment of patients with concurrent prophylaxis use if the number of patients exceeds approximately 1/3.

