5.5.1.4. Analysis Populations

There were 4 analysis populations defined:

Intent-to-Treat (ITT) Population: All patients who are randomized and receive at least 1 dose of study drug.

Safety Population: This population is the same as the ITT population defined above.

Open-label treatment population: All patients who enter the open-label treatment phase (Study Period IV) as indicated by receiving any injections starting from V isit 7. Patients in the open-label treatment population will be analyzed as a single group as they start with the same dose in the study period. Analyses for open-label phase only will be based on open-label treatment population.

Post-treatment Population: All patients who enter the post-treatment phase (Study Period V) as indicated by entering any post-treatment visit (telephone or office visit). Analyses for post-treatment phase only (that is, excluding earlier study periods) will be based on post-treatment population.

Unless otherwise stated, all analyses will be analyzed according to the ITT principle on the ITT population. That is, patients will be analyzed according to the treatment they were randomized to, regardless of whether they actually received a different treatment.

Safety analyses (Section 5.5.1.2) and analyses for disposition and exposure will be conducted based on the modal treatment group patients have received (Placebo, LY120mg, or LY240mg) during the double-blind Study Period from the first to last injections at Visit 3 through Visit 6. For determining modal dose, do not consider the loading dose visit for subjects assigned to an LY120mg treatment group; do consider it for subjects assigned to the Placebo and LY240mg treatment groups. If there are 2 or more modes, then add the loading dose visit and recalculate the mode, if any. If a tie still remains, the highest LY dose of the modes will be used.

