The analysis of elevation in ALT, AST, ALP, and TBIL will contain 3 subsets:

 patients whose nonmissing maximum baseline value is less than or equal to 1× ULN for ALT, AST, ALP, and TBIL.

- patients whose nonmissing maximum baseline value is greater than 1× ULN for ALT, AST, ALP, and TBIL, at the same time less than or equal to 2× ULN for ALT and AST, 1.5× ULN for ALP and TBIL.
- patients whose nonmissing maximum baseline value is greater than 2× ULN for ALT and AST, 1.5× ULN for ALP and TBIL.

5.5.12.1.6. *Immunogenicity*

To evaluate the changes in immunogenicity data (Anti-LY2951742 [ADA and NAb]) after treatment, the following statistical analyses are planned for comparison between treatment groups:

- The incidence of ADA positive during baseline will be summarized.
- The incidence of treatment-emergent ADA (TE ADA) between treatment groups will be summarized and compared for SP III. The incidence of TE ADA for LY-treated patients during LY treatment and the incidence of TE ADA for LY-treated patients during LY treatment and post-treatment phase combined will be summarized. This analysis will be done for each immunogenicity analyte (ADA and NAb). The baseline and postbaseline definitions for each Study Period is shown in Table CGAI.5.4. Treatment-emergent ADA will be defined as any of the following:
 - o a negative baseline result and a positive postbaseline ADA result with a titer ≥20. This is also called treatment-induced ADA.
 - a positive baseline result and a positive postbaseline ADA result with a ≥4-fold increase in titers (for example, baseline titer of 10 increasing to ≥40 postbaseline). This is called treatment-boosted ADA.
- The incidence of TE ADA and NAb Positive combined between treatment groups will be summarized for the same time periods as planned for the incidence of TE ADA.

The following will also be provided:

- Listing of subjects with TE ADA at any time during study, NAb Status will also be displayed.
- Listing of subjects with ADA detected at any time during study, excluding subjects with TE ADA.
- Line plot of ADA titers over time for each subject with TE ADA at any time.
- Listing of subjects with TE hypersensitivity reactions or TEAEs related to injection sites for subjects with ADA present at any time.

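### The ADA baseline stays at Visit 3 in every period after SP III, although placebo-randomized patients are first exposed to LY2951742 at Visit 7

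*SAP*

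**What the plan says.** The SP IV row of SAP Table CGAI.5.4 (section 5.5.1.5) reads "Treatment-emergent immunogenicity Open Label treatment Population Visit 3 All Visits 7.01–16". The rows labelled "Treatment-emergent immunogenicity" for SP V, SP III/IV and SP III/IV/V also give Visit 3 as baseline.

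Placebo patients begin LY2951742 in the extension. The footnote to the SAP design figure says "At Visit 7, all patients who enter the open-label extension will receive LY2951742 at a dose of 240 mg". SAP section 5.5.1.4 adds "Patients in the open-label treatment population will be analyzed as a single group as they start with the same dose in the study period".

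SAP section 5.5.12.1.6 defines treatment-induced ADA as "a negative baseline result and a positive postbaseline ADA result with a titer ≥20", and treatment-boosted ADA as a rise of at least 4-fold in titer from a positive baseline. Among its planned results is "The incidence of TE ADA for LY-treated patients during LY treatment". For baseline and postbaseline it refers to Table CGAI.5.4 and makes no exception for patients who start LY2951742 at Visit 7.

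The Schedule of Activities (Protocol Appendix 2) has an immunogenicity sample at Visit 7. Its footnote, which covers immunogenicity, storage and "PK blood sampling to be performed at the indicated visits and prior to dose administration if the visit is a dosing visit", puts that sample ahead of the first open-label injection.

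**The concern.** A treatment-emergent event should be judged against the patient's state before the treatment to which it is attributed. Visit 3 serves that purpose for LY-randomized patients. For placebo-randomized patients it lies three months before first exposure, and the matching sample is the one taken before dosing at Visit 7.

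The other SP IV rows that use a baseline all run through Visit 7. The adverse-event row, for example, reads "TEAEs Open Label treatment Population All Visits 1-7 All Visits 7.01–16". The immunogenicity row has reason to differ for LY-randomized patients, but not for former placebo patients.

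At stake is the incidence of drug-emergent ADA. It bears on a stated objective (the development and consequences of ADA), and the SAP relates it to hypersensitivity and injection-site events. The same conversion could appear as placebo background in the SP III table and as LY2951742-emergent in a later one.

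**Working it through.** The documents give no ADA incidence or placebo conversion rate, so there is no planned figure to reproduce. The check has two parts.

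**1. The rule applied to example patients**

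Inputs are the definitions in SAP 5.5.12.1.6 and the SP IV window of Visits 7.01–16. All examples are placebo-randomized patients first dosed at Visit 7. The titers are illustrative.

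| Visit 3 | Before Visit 7 dose | On drug | TE ADA, Visit 3 baseline | TE ADA, Visit 7 baseline |
|---|---|---|---|---|
| negative | 40 | 40 | yes | no |
| negative | 10 | 20 (2-fold) | yes | no |
| negative | negative (40 at Visit 6) | negative | no | no |
| negative | 10 | 10 | no | no |
| negative | 20 | 80 (4-fold) | yes | yes |
| 40 | negative | 20 | no | yes |

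Rows 1 and 2 are false positives under the Visit 3 baseline, and row 6 is a false negative. Row 5 shows that a true boost survives the change of baseline. Row 3, the transient conversion, is not counted in SP IV because the window opens after Visit 7. In SP III/IV (Visits 3.01–16) and SP III/IV/V (Visits 3.01–18), its Visit 6 titer of 40 would qualify on the table's wording alone.

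**2. Possible size in the pooled open-label group**

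- Placebo arm: 1140 × 2/4 = 570, which agrees with SAP 5.2. The two LY2951742 arms together also have 570.
- Entry to SP IV: assume 85% of each arm. This borrows the 15% discontinuation assumption in SAP 5.2 and supposes that every completer continues. Former placebo = 570 × 0.85 = 484.5; open-label total = 1140 × 0.85 = 969.
- Conversion on placebo, q: assumed 0.5–5%.
- Share still qualifying after Visit 7, f: assumed 25–100%.

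False positives = 484.5 × q × f. Pooled inflation is that count divided by 969. Inflation among former placebo patients is q × f.

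| q | f | False positives | Pooled, points | Former placebo, points |
|---|---|---|---|---|
| 0.5% | 25% | 0.6 | 0.06 | 0.125 |
| 2% | 50% | 4.8 | 0.50 | 1.0 |
| 5% | 100% | 24.2 | 2.5 | 5.0 |

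If the denominator is instead everyone ever given LY2951742, it becomes 570 + 484.5 = 1054.5, and the top of the range falls to 24.2/1054.5 = 2.3 points. These figures do not net off false negatives of the row 6 kind. They also ignore false positives who would have qualified on drug anyway, and that overlap would lower them.

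**The case against.** The strongest reply is that the plan already exposes the problem. TE ADA is compared between arms in SP III, with placebo included and Visit 3 as the right baseline, so the placebo conversion rate will be reported. A listing and a titer-over-time plot are planned for each patient with TE ADA, where someone already positive before the Visit 7 dose can be picked out. SP IV and SP V results are descriptive only. All of this stands and limits the risk of a wrong conclusion, but none of it corrects the incidence that is tabulated.

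It can also be said that Visit 3 is a deliberate choice, being the only drug-naive sample for LY-randomized patients. That is right, and moving everyone to Visit 7 would be an error. The gap concerns former placebo patients only.

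A third reply is that 5.5.12.1.6 already confines the result to time on LY2951742. That wording limits the period and, if programmed as a filter, would remove transient conversions from the combined rows. It leaves the baseline unchanged.

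A reader might go further than the documents allow in three ways:

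- That every placebo-period conversion is counted as drug-emergent. In the SP IV row only those still qualifying after Visit 7 are.
- That the bias is always upward. Row 6 of the first table runs the other way.
- That half the open-label group is affected. The one-half is the randomized split; entry to SP IV is optional and follows completion of SP III, so the open-label split is not known.

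**Conclusion.** The point holds as a defect in the baseline definition. Followed as written, Table CGAI.5.4 attributes persistent placebo-period conversions to LY2951742 in SP IV and SP V. It admits transient ones in the combined periods unless a filter is added, and it can miss some on-drug conversions.

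The size cannot be determined from the documents. The range of 0.06–2.5 percentage points of pooled open-label incidence rests entirely on the assumed conversion, persistence and entry rates, and its low end is negligible. A reader might want to state a relative excess over the true incidence, but no true incidence is given and any such percentage would be an artefact of the value chosen.

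Nor do the documents support a wider charge against the safety analysis. The randomized SP III ADA comparison has the correct baseline. Hypersensitivity is related to TE ADA within LY2951742 dose groups, so that work is touched only if open-label data from former placebo patients are pooled in. Efficacy is not involved. The change should be made, but the trial's main conclusions do not depend on it.

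**What to change.** In Table CGAI.5.4, for summaries of LY-treated patients in SP IV, SP V, SP III/IV and SP III/IV/V:

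- Define the ADA baseline as the last sample before the first LY2951742 dose. That is Visit 3 for LY-randomized patients and the pre-dose Visit 7 sample for placebo-randomized patients, or their last earlier sample if Visit 7 is missing.
- Start the postbaseline window after that first dose. This matters for the two combined rows, which now open at Visit 3.01 for everyone.
- Repeat both rules in section 5.5.12.1.6, so that the restriction to time on LY2951742 is an explicit derivation.

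Keep Visit 3 for the randomized SP III comparison. Placebo patients who go from SP III straight to follow-up never receive LY2951742 and fall outside these summaries.

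The cost is revised SAP wording and one derived baseline flag. No visit, sample or assay is added, because the Visit 7 pre-dose sample is already scheduled.
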